^b Weekly visit may be omitted if Visit Y is within 2 days of weekly visit.

Visit Y is only utilised if the dosing schedule is intermittent. Visit Y represents the last AZD7648 dosing day in the first block of AZD7648 treatment in a cycle eg, CCI

^d There are no visit windows in Cycle 0 and Cycle 1.

^e With the patient's consent, as part of the medical history, any available information on known tumour gene mutations will be collected.

^f Targeted physical examinations only required if clinically indicated (indication should be stated).

^g Vital signs then ECG measurements will be collected prior to PK blood draws at all PK sample timepoints. Timepoints may be modified based on initial data obtained.

- ^h Serious adverse events (SAEs) only to be collected between AZD7648 discontinuation and disease progression
- ⁱ Women of child-bearing potential must have a negative urine or serum pregnancy test at screening, a confirmatory test before treatment on Day 1 (Cycle 0 or Cycle 1), at regular intervals during treatment and at AZD7648 discontinuation. If results are positive, the patient is ineligible/must be discontinued from study treatment and not discontinued from the study. The patient will continue to be followed up according to the study protocol.
- ^j TSH to be measured at baseline and every 3 cycles. CRP to be collected at baseline, then on Day 1 from Cycle 1. Urinalysis at Cycle 0, Cycle 0+1 and Day 1 of each cycle. Tumour markers (if relevant) to be measured at baseline and on Day 1 of every cycle from Cycle 1 (only if elevated at baseline).
- ^k Provision of archival tumour samples is mandatory for all patients. The samples may be submitted retrospectively.
- ¹ Fresh biopsy samples are encouraged in Part A (particularly in patients with accessible tumours) and are mandatory for patients enrolled into Part A PD expansion cohorts (or a PD subgroup of an efficacy expansion cohort). Serial biopsies will be collected during screening, on treatment (any time in Cycle 1 between Day 3 and Day 8 [or Y] 2 to 8 hours [h] post AZD7648 dosing), and on progression.

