8.3.2 Time period and frequency for collecting AE and SAE information

AEs will be collected from time of signature of ICF throughout the treatment period and including the 28-day follow-up visit after treatment discontinuation.

All SAEs will be recorded from the time of signing of ICF until the 28-day follow-up visit after treatment discontinuation. Only SAEs related to the study treatment and/or procedure will be recorded thereafter (during the progression follow-up).

All SAEs will be recorded and reported to the Sponsor or designee within 24 hours, as indicated in Appendix B. The Investigator will submit any updated SAE data to the Sponsor within 24 hours of it being available.

Investigators are not obligated to actively seek AE or SAE in former study patients. However, if the Investigator learns of any SAE, including a death, at any time after a patient's last visit and he/she considers the event to be reasonably related to the study treatment or study participation, the Investigator may notify the Sponsor.

The method of recording, evaluating, and assessing causality of AE and SAE and the procedures for completing and transmitting SAE reports are provided in Appendix B.

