9.4.2 Safety analyses

These are primary variables.

All safety analyses will be performed on the safety analysis set. All patients who receive at least 1 dose of study treatment will be included in the assessment of the safety profile. At the end of the study, appropriate summaries of all safety data will be produced, as defined below.

Data from all cycles of initial treatment will be combined in the presentation of safety data. AEs will be listed individually by patient and cohort. For patients who have a dose modification, all AEs (due to drug or otherwise) will be assigned to the initial dose group. The number of patients experiencing each AE will be summarised by the Medical Dictionary for Regulatory Activities (MedDRA) system organ class, MedDRA preferred term and CTCAE grade. The number and percentage of patients with AEs in different categories (eg, causally related, CTCAE Grade \geq 3 etc) will be summarised by dose regimen, and events in each category will be further summarised by MedDRA system organ class and preferred term, by dose group. SAEs will be summarised separately.

Any AE occurring before the first dose of study treatment (ie, before study Day 1) will be included in the data listings but will not be included in the summary tables of AEs. Treatment-emergent AEs occurring prior to first dose of investigational product (ie, before study Day 1) which subsequently worsen in severity following dosing will be included in the summary tables.

Any AE occurring within the defined 28-day follow-up period after discontinuation of study treatment will be included in the AE summaries. Any AEs in this period that occur after a patient has received further therapy for cancer (following discontinuation of study treatment) will be flagged in the data listings. AEs occurring after the 28-day follow-up period after discontinuation of study treatment will be listed separately, but not included in the summaries.

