15.1 Management of study treatment-related toxicities

At this time, there are limited safety data regarding the combination of AZD7648 and PLD. Given the differing mechanisms of action of AZD7648 and PLD, the potential for potentiation of toxicities is thought to be limited. Some toxicities, for example pneumonitis and asthenia/fatigue may, on theoretical grounds, be potentiated in the combination arm and particular attention should be paid to these.

In the event of toxicity in this combination module of the study which cannot be managed by supportive measures alone, stopping one or both study treatments should be an Investigator decision based on the available information and, if necessary, following discussion with the Sponsor.

The following general guidance should be followed for management of toxicities:

- Treat each of the toxicities with maximum supportive care (including withholding the agent suspected of causing the toxicity if required).
- If the symptoms promptly resolve with supportive care, consideration should be given to continuing the same dose of the assigned study treatment along with appropriate continuing supportive care. If medically appropriate, dose modifications are permitted for AZD7648. In addition, guidelines on AZD7648 dose modifications are provided in Section 6.6 and 14.4. In the event of toxicity that cannot be managed by following the toxicity management guidelines for AZD7648 and PLD, consider stopping treatment.

All dose modifications should be documented with clear reasoning and documentation of the approach taken.

Management of PLD related toxicities will be performed in accordance with local practice.

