3.2.1.4 Adverse Events

Adverse events (AEs) and serious adverse events (SAEs) will be collected throughout the study, from date of informed consent until 28 days after the last dose of study treatment. Events will be defined as treatment emergent if they onset, or worsen (by investigator report of a change in intensity), during the

treatment period starting from the first dose on cycle 0, day 1 or during the 28-day safety follow-up period. Any events in this period that occur after a patient has received further therapy for cancer (following discontinuation of study treatment) will be flagged in the data listings. The latest version of MedDRA will be used to code the AEs. AEs will be graded according to the National Cancer Institute of Common Terminology Criteria for AEs (CTCAE version 5.0 or higher).

In general, all AE summary tables include only treatment emergent AEs. AEs occurring prior to dosing or starting more than 28 days after discontinuation of study drug will be flagged in listings and will not be included in any summaries.

All reported AEs will be listed along with the actual treatment received at the time of onset, date of onset, date of resolution (if AE is resolved), investigator's assessment of CTCAE grade, relationship to study treatment, action taken and outcome. Frequencies and percentages of patients reporting each preferred term will be presented (i.e., multiple events per patient will not be accounted for, except for event level summaries).

Summaries of adverse events (the number and percentage of patients by treatment) by MedDRA System Organ Class (SOC) and Preferred Term (PT) will include but are not limited to:

- All AEs.
- All AEs possibly related to study treatment.
- AEs of CTCAE grade 3 or higher.
- AEs of CTCAE grade 3 or higher, possibly related to treatment.
- AEs with outcome of death.
- All SAEs.
- All SAEs possibly related to study treatment.
- AEs leading to discontinuation of treatment.
- AEs leading to discontinuation of treatment, possibly related to treatment.
- SAEs leading to discontinuation of treatment.
- SAEs leading to discontinuation of treatment, possibly related to treatment.

Other significant adverse events (OAE)

No OAEs are planned to be defined for this study.

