Any AE occurring within the defined 28 days follow-up period after discontinuation of investigational product will be included in the AE summaries. Any adverse events in this period that occur after a patient has received further therapy for cancer (following discontinuation of investigational product) will be flagged in the data listings. TEAEs occurring prior to first dose of investigational product (ie, before study Day 1) which subsequently worsen in severity following dosing will be presented in the summary tables. All other AEs occurring prior to first dose of investigational product (ie, before study Day 1), or after the 28 days follow-up period after discontinuation of investigational product will be listed separately, but not included in the summaries.

Fluctuations observed in CTCAE grades during study will be listed (where collected). When assigning a maximum CTCAE grade to a TEAE, only grade changes occurring after the date of first dose of study treatment and up to 28 days after the last dose of study treatment will be considered.

Details of any deaths will be listed for all patients.

Haematology and clinical chemistry results will be summarised using descriptive statistics (mean, median, standard deviation, minimum, maximum and number of observations). For all laboratory variables included in the current version of CTCAE, the CTCAE grade will be summarised. The post-baseline results and its change from baseline for laboratory, ECG, vital signs data at each timepoint will be summarised. For all haematology and clinical chemistry results, change from baseline will be plotted using a spaghetti plot. Creatinine clearance and echocardiogram (LVEF) results at different timepoints and their change from baseline will be summarised using descriptive statistics. Creatinine clearance and echocardiogram (LVEF) results will be listed as well by visit. LVEF will also be summarised by categories listed in section 3.2.1.12. All abnormal findings from the physical exam will be listed. The number of patients for each ECOG-PS grade will be presented.

For the core module, individual 4 β -hydroxy cholesterol concentration data will be listed only.

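### Footnote h of the assessment schedules restricts collection to SAEs once AZD7648 stops, contradicting the all-AE rule through the 28-day follow-up in protocol Section 8.3.2 and the SAP

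*Protocol*

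**What the plan says.** In protocol Table 1 (Core Module) and Table 13 Parts A and B (Combination Module 1), the AE row has superscript h at the investigational product discontinuation visit. Footnote h reads: "Serious adverse events (SAEs) only to be collected between AZD7648 discontinuation and disease progression". In the next column, the 28-day follow-up visit, the AE entry is an X with no footnote. The row refers the reader to Section 8.3.

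Protocol Section 8.3.2 gives a different rule: "AEs will be collected from time of signature of ICF throughout the treatment period and including the 28-day follow-up visit after treatment discontinuation". All SAEs follow the same period. After that visit, recording is limited to SAEs related to study treatment or procedures.

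The analysis text agrees with Section 8.3.2. Protocol Section 9.4.2 states: "Any AE occurring within the defined 28-day follow-up period after discontinuation of study treatment will be included in the AE summaries". SAP Section 3.2.1.4 describes AEs and SAEs as collected "from date of informed consent until 28 days after the last dose of study treatment" and treats events in the 28-day safety follow-up as treatment emergent. SAP Section 4.2.1 repeats: "Any AE occurring within the defined 28 days follow-up period after discontinuation of investigational product will be included in the AE summaries".

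AEs and SAEs are the first variables listed under the primary objective (protocol Section 3), and Section 9.4.2 labels the safety variables as primary.

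**The concern.** The analysis assumes that non-serious AEs are fully observed for 28 days after treatment stops. Footnote h, taken as written, tells sites to stop recording them on the day AZD7648 stops, for as long as the patient has not progressed. A site that follows the footnote and a site that follows Section 8.3.2 are both following the protocol, yet they would deliver different data for the same window.

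The patients exposed are those who discontinue before progression, including those who stop for toxicity. Late or persisting non-serious events are of most interest in that group. SAP Section 1.1 says the reporting was reduced to focus mainly on safety after development was halted, so completeness of AE data carries most of the weight in the final report.

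**Working it through.** No sample size, power or test is involved, and the plan gives no figure to reproduce. The check compares the rules and works out how long they overlap.

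**1. The rules side by side**

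| Source | From | What is collected or counted | Until |
|---|---|---|---|
| Footnote h, Tables 1, 13A, 13B | AZD7648 discontinuation | SAEs only, related or not | Disease progression |
| AE row, 28-day column, same tables | 28-day visit | AEs, no restriction marked | 28-day visit |
| Protocol 8.3.2, first rule | Consent | All AEs and SAEs | 28-day visit after discontinuation |
| Protocol 8.3.2, second rule | 28-day visit | Related SAEs only | Progression follow-up |
| Protocol 9.4.2; SAP 4.2.1 | First dose | Any AE enters the summaries | 28 days after discontinuation |
| SAP 3.2.1.4 | Consent | AEs and SAEs | 28 days after last dose |

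The footnote is the only entry that excludes non-serious AEs between discontinuation and the 28-day visit.

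**2. Length of the conflict**

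Let T be the days from AZD7648 discontinuation to progression, and V the day of the 28-day visit. V is nominally 28, with a ±7-day window in the schedules, so the latest day is 28 + 7 = 35. The period in which footnote h excludes what Section 8.3.2 requires is min(V, T):

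- Stops at or after progression (T = 0): min(28, 0) = 0 days.
- Visit on day 28, progression on or after day 28: 28 days.
- Visit on day 35, progression on or after day 35: 35 days.

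For the AE summaries the exposed period is at most 28 days, because the SAP does not summarise events starting later than that.

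**3. Can the footnote be read so that the conflict disappears?**

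Suppose h is meant to apply only after the 28-day visit. It does not say so. Even then it asks for all SAEs to progression, which agrees with Section 8.4.1 (SAEs are reported whether or not considered related) but not with Section 8.3.2 (related SAEs only). A mismatch remains on either reading.

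**4. Does one text take precedence?**

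Section 8 makes adherence to the schedule a requirement of study conduct, and Section 8.2 sends readers to the schedule for the timing of safety assessments. The precedence statements elsewhere concern eligibility cut-offs (Section 5) and crisis measures (Section 4.1.4). Nothing ranks the footnote against Section 8.3.2.

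**The case against.** The best case for the plan is that only one footnote is out of line. The 28-day column has an unfootnoted AE mark, the row points to Section 8.3, and four other passages agree on the 28-day window. Section 8.3.6 has sites ask about health problems since the patient was last asked, so an AE assessment at the 28-day visit looks back over the whole interval. On this view h describes progression follow-up, which has no column of its own.

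Much of this stands. It makes loss of events less likely, and no passage shows that any site followed the footnote in preference to Section 8.3.2. It does not remove the contradiction: the footnote names the interval and starts it at discontinuation, and a schedule that needs its own footnote ignored is not a clear instruction.

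Three stronger readings are tempting but not supported:

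- **Every patient loses 28 days.** The footnote ends at progression, which is also the first-listed reason for stopping treatment (Section 7.1). Only patients who stop before progression are exposed.
- **The gap is a stated share of the treatment-emergent period.** That requires treatment durations the documents do not give, and it would measure calendar time, not missed events.
- **Patients who stay on PLD drop to SAE-only collection while on treatment.** The footnote is keyed to AZD7648, and Section 15.1 says "stopping one or both study treatments should be an Investigator decision", so a reader might infer this. However, the continuation routes actually described (Sections 12.1, 14.1.2 and 14.4) are AZD7648 without PLD. The AE entries at the on-treatment visits carry no footnote, and Section 8.3.2 covers the treatment period.

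**Conclusion.** The contradiction holds and should be corrected. Footnote h conflicts with protocol Sections 8.3.2 and 9.4.2, with SAP Sections 3.2.1.4 and 4.2.1, and with the schedules' own entry at the 28-day visit.

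Its size is bounded. For a patient who stops AZD7648 before progression, non-serious AEs could go unrecorded for up to min(28 days, time to progression), or up to 35 days of collection if the visit is at the end of its window. Patients who stop at or after progression are unaffected. DLT counts are largely untouched because DLTs are assessed in Cycles 0 and 1, although a patient who stops AZD7648 in that period could be affected.

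This rests on a literal reading of the footnote by at least some sites. The documents do not give the share of patients who stop before progression or the number of events that might be missed, so no estimate of lost events can be made.

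**What to change.** Reword footnote h in Table 1 and in Table 13 Parts A and B. It should say that all AEs and SAEs are collected through the 28-day follow-up visit after discontinuation of study treatment, and that the SAE-only period begins after that visit. For Combination Module 1, discontinuation should mean the last of AZD7648 or PLD, in line with the definition of study treatment in Section 14.

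Separately, reconcile what is recorded from then to progression: all SAEs, as footnote h and Section 8.4.1 have it, or only related SAEs, as in Section 8.3.2. The rewording should not settle this by default.

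The cost is one footnote in three schedules. Part B is outside the final SAP scope (SAP Section 1.2), so the change there is for consistency. If no further amendment is planned, the sponsor can ask sites which rule they applied and report the answer in the CSR next to the AE summaries.

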1.2 Synopsis

Principal Investigator:

[name] [name]

Protocol Title:

A Phase I/IIa, Open-Label Study to Assess the Safety, Tolerability, Pharmacokinetics and Preliminary Efficacy of Ascending Doses of AZD7648 Monotherapy or in Combination with either Cytotoxic Chemotherapies or Novel Anti-Cancer Agents in Patients with Advanced Malignancies

Rationale:

In cancer cells, defective DNA damage response (DDR) promotes genomic instability, neoplastic transformation and proliferation. Such instability results in the formation of highly destructive double-strand breaks (DSBs) and cell death. DNA dependent protein kinase (DNA-PK) overexpression renders tumours resistant to DNA damage; therefore DNA-PK inhibition is an attractive therapeutic strategy. Preclinical data from both in vitro and in vivo systems supports this hypothesis and provides the rationale required to explore the clinical potential of the DNA-PK selective inhibitor AZD7648.

Study Design:

This is a modular Phase I/IIa, open-label, multi-centre, study of AZD7648 administered orally, either as a monotherapy, or in combination with either cytotoxic chemotherapies or novel anti-cancer agents in patients with advanced malignancies. The modular design allows for an escalation of the dose of AZD7648 alone or in combination with either cytotoxic chemotherapies or novel anti-cancer agents, with intensive safety monitoring to ensure the safety of the patients.

The study consists of 2 modules each evaluating the safety and tolerability of AZD7648 monotherapy or with a specific combination partner. The initial components are a Core Module of AZD7648 monotherapy and Combination Module 1 (AZD7648 in combination with pegylated liposomal doxorubicin [PLD]). Up to 5 additional combination modules may be added via a formal amendment (see Section 4.1.3) to allow further evaluation of AZD7648 in defined populations or novel combinations. These may include i) combination with a DDR agent eg, ataxia telangiectasia and Rad3-related protein (ATR) inhibitor; ii) combination with an immuno-oncology agent eg, a programmed death-ligand 1 (PD-L1) inhibitor; iii)

combination with a cytotoxic agent eg, paclitaxel; iv) combination with an antibody-drug conjugate; and v) combination with radiotherapy.

Combination Module 1 has 2 study parts: Part A consisting of dose escalation cohorts and Part B, a safety and proof of concept (PoC) Phase IIa expansion. Part A dose escalation and de-escalation will follow the principles of the Bayesian adaptive design which combines prior expectations about the dose toxicity relationship and applies the data at the end of each cohort to recommend a dose for the next cohort. A Safety Review Committee (SRC) will review evaluable patients at each cohort and assess if the study should progress to Part B. Optional expansion cohorts may also be triggered in Part A dose escalations, enrolling additional patients at appropriate dose(s) to explore further the safety, tolerability, pharmacodynamics (PD), pharmacokinetics (PK), biological activity and effect of food.

Main Objectives:

The primary objective is to investigate the safety and tolerability of AZD7648 when given orally to patients with advanced malignancies, as monotherapy and in combination with anti-cancer agents, and to define the doses and schedules for further clinical evaluation.

Secondary objectives are i) to characterise the PK of AZD7648, following a single dose and at steady state after multiple doses, when given orally as monotherapy and in combination with anti-cancer agents, and to characterise the effect of food on AZD7648 exposure (if conducted); ii) to obtain a preliminary assessment of anti-tumour activity of AZD7648 as monotherapy and in combination with anti-cancer agents.

Tertiary/exploratory objectives are described in Section 3.

Study Period:

Estimated date of first patient enrolled: Q4 2019

Estimated date of last patient completed: Q2 2024

Number of Patients:

Approximately 192 evaluable patients may be enrolled in the Core Module (95 evaluable patients: 46 patients in the dose escalation and up to 49 additional patients in optional expansion cohorts) and Combination Module 1 (97 evaluable patients: 30 patients in the dose escalation with the potential for an additional 30 patients once maximum tolerate dose [MTD] has been determined, and 37 patients in the expansion cohort).

Treatments and Treatment Duration:

For the Core Module, a single dose of AZD7648 will be administered in the clinic (Cycle 0, Day 1) to enable collection of blood samples for PK analyses. This will be followed by a drug washout (no dose) of 3 to 7 days prior to Cycle 1, Day 1 AZD7648 administration.

In cohort 1, at Cycle 1, Day 1, the starting dose of AZD7648 will be mg CCL and on a continuous CCL and the starting dose of AZD7648 will be mg CCL and a continuous CCL and the starting dose of a context between cycles. Using an accelerated titration design, dose escalation may occur with single patient cohorts up to and including mg CCL and the mg CCL and the mg CCL and the maximum of 3 patients will be enrolled into each dose cohort. Dose escalation will stop at the MTD, maximum feasible dose (MFD), or the recommended Phase II dose (RP2D). From Cohort 2 onwards, intermittent dosing schedules for AZD7648 may be explored.

For Combination Module 1 the starting dose of AZD7648 is dependent on emerging safety and tolerability data from the Core Module. Intermittent dosing schedules for AZD7648 may be explored.

For Combination Module 1 the starting dose of PLD is 40 mg/m², administered by intravenous (IV) infusion once every 4 weeks, for a maximum of 6 cycles. AZD7648 will be administered 4 hours from the start of the IV infusion of PLD.

